8.3.1. Adverse Events

Adverse events that begin or worsen after informed consent should be recorded on the Adverse Events Form in the eCRF regardless of the assumption of a causal relationship with the study treatment. Conditions that were already present at the time of informed consent should be recorded on the Medical History Form in the eCRF. Adverse events (including laboratory abnormalities that constitute AEs) should be described using a diagnosis whenever possible rather than by individual underlying signs and symptoms.

Adverse events will be reported by the participant (or, when appropriate, by a caregiver, surrogate, or the participant's legally authorized representative). The investigator and any qualified designees are responsible for detecting, documenting, and recording events that meet the definition of an AE or SAE and remain responsible for following-up on AEs that are serious, considered related to the study treatment/procedures, or that caused the participant to discontinue the study treatment. Care will be taken not to introduce bias when detecting AEs and/or SAEs. Open-ended and nonleading verbal questioning of the participant, such as "How are you feeling?" is the preferred method to inquire about AE occurrences. Adverse events may also be detected when they are volunteered by the participant during the screening process or between visits or through physical examinations, laboratory tests, or other assessments. The definition, reporting, and recording requirements for AEs are described in Section 9.

All SAEs will be reported to the sponsor or designee within 24 hours. The investigator will submit any updated SAE data to the sponsor within 24 hours of it being available.

After the initial AE/SAE report, the investigator is required to proactively follow each participant at subsequent visits/contacts. All SAEs, nonserious AEs, and AESIs (as defined in Section 9.5.1), will be followed until resolution, stabilization, the event is otherwise explained, or the participant is lost to follow-up (as defined in Section 7.3).

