9.4. Reporting of Serious Adverse Events

Regardless of suspected causality (eg, relationship to study treatment or study procedure[s]), all SAEs occurring after the participant has signed the ICF through completion of the study *or* until the participant starts a new anticancer therapy (whichever occurs earlier) must be reported to the sponsor (or designee) within **24 hours** of learning of its occurrence, unless otherwise specified by the Protocol. The investigator will submit any updated SAE data to the sponsor (or designee) immediately, without undue delay but not later than within 24 hours of it being available. For Japan, this information must also be reported immediately to the head of the study site in Japan.

Investigators are not obligated to actively seek SAE information after the EOT visit. If the investigator learns of any SAE, including a death, at any time during this period, and he/she considers the event to be reasonably related to the study treatment or study participation, then the investigator must notify the sponsor (or designee) within 24 hours of becoming aware of the event.

After the initial AE/SAE report, the investigator is required to proactively follow each participant at subsequent visits/contacts. All SAEs and AESIs (as defined in Section 9.5.1) will be followed until resolution, stabilization, the event is otherwise explained, or the participant is lost to follow-up (as defined in Section 7.3).

Prompt notification by the investigator to the sponsor regarding an SAE is essential so that legal obligations and ethical responsibilities towards the safety of participants and the safety of a study treatment under clinical investigation are met.

If the SAE is not documented in the RSI of the IB or product information for study treatment (new occurrence) or marketed products, respectively, and is thought to be related to the study treatment, the sponsor or its designee may urgently require further information from the investigator for expedited reporting to health authorities. The sponsor or its designee may need to issue an Investigator Notification to inform all investigators involved in any study with the same drug that this SAE has been reported. SUSARs will be collected and reported to the competent authorities and relevant ethics committees in accordance with Directive 2001/20/EC or as per national regulatory requirements in participating countries.

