8.2.2. Adverse Events of Special Interest by eCRF

The number (%) of participants who had an AESI, the time to onset of each AESI, and the longest duration of each AESI will be summarized by treatment group.

Whether an AE is an AESI and which AESI it is can be found in the "Adverse Event" eCRF form. This information will be used to identify AESIs.

Adverse events of special interest for tafasitamab/placebo include TLS, IRRs and allergic reactions to study drug ≥ Grade 3, CRS, SPMs, hepatitis B reactivation, and PML.

Adverse events of special interest for lenalidomide include SPMs.

The longest duration of an AESI is defined as the longest interval between the date of occurrence of an AESI and the date of resolution. If participants have a missing or partial onset/end date of an AESI, the partial or missing dates will be handled using the rules explained in Section 4.1.4. Participants who have a missing end date of an AESI at the time of analysis will be right-censored using the following algorithm:

- If the AESI is serious, then the participant will be censored at the earlier date of data cutoff, study discontinuation, or death.
- If the AESI is not serious,
 - If the participant is ongoing with study treatment, then the participant will be censored at the data cutoff date.
 - If the participant discontinued treatment, then the participant will be censored at date of safety follow-up visit, or 90 days after the EOT visit (or after the last dose if the EOT visit was not performed), whichever is later; the censored date will be truncated by the earlier date of data cutoff, study discontinuation, or death if beyond.

The Kaplan-Meier estimate of median time to resolution/improvement and its 95% CIs will be provided, with the CIs calculated using the generalization of Brookmeyer and Crowley's method (1982) with log-log transformation (Klein and Moeschberger 1997). Resolution/improvement rates at selected timepoints will also be provided with 95% CIs calculated using Greenwood's formula to estimate the standard error. Such analysis for an AESI will not be conducted if 10 or fewer participants had the AESI.

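### For nonserious AESIs in participants off treatment, SAP 8.2.2 censors unresolved events at about EOT + 90 days but counts later resolutions at full length, so late Kaplan-Meier resolution rates can be biased upward

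*SAP*

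**What the plan says.** SAP 8.2.2 defines duration by the resolution date: "The longest duration of an AESI is defined as the longest interval between the date of occurrence of an AESI and the date of resolution". Censoring applies only where that date is absent: "Participants who have a missing end date of an AESI at the time of analysis will be right-censored". There are then three branches.

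- Serious AESI: "If the AESI is serious, then the participant will be censored at the earlier date of data cutoff, study discontinuation, or death".
- Nonserious, on treatment: "If the participant is ongoing with study treatment, then the participant will be censored at the data cutoff date".
- Nonserious, treatment discontinued: "If the participant discontinued treatment, then the participant will be censored at date of safety follow-up visit, or 90 days after the EOT visit", whichever is later, truncated at data cutoff, study discontinuation or death. I read this branch as also covering participants who completed the 12 cycles, because the rule offers them no other.

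The outputs are a Kaplan-Meier median and more: "Resolution/improvement rates at selected timepoints will also be provided". The timepoints are not named. The analysis is skipped for an AESI seen in 10 or fewer participants. SAP 8.2.3 applies the same method to AESIs identified by category and preferred term.

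On data collection, Protocol 8.3.1 says: "All SAEs, nonserious AEs, and AESIs (as defined in Section 9.5.1), will be followed until resolution", or stabilization. Protocol 9.4 says: "All SAEs and AESIs (as defined in Section 9.5.1) will be followed until resolution, stabilization, the event is otherwise explained". Protocol 9.3 (follow-up part) and 7.1.2 also extend follow-up to resolution or to a judgement that the event is permanent. Protocol 8.3, the recording part of 9.3, and Table 3 instead tie AE recording to the 90-day safety follow-up.

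**The concern.** Kaplan-Meier estimation needs censoring that carries no information about the later outcome. Here, take two nonserious AESIs still open at the end of the window. The one that resolves six months later has an end date, stays in the risk set and counts as an event. The one that never resolves is removed at the window. Past that point, continued presence in the risk set is decided by the future outcome.

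The resolution rates are the planned description of how reversible the AESIs are. If the late part of the curve is inflated, lasting events look more reversible than they are. The exposed period is long: treatment lasts up to 12 × 28 = 336 days, while SAP 9.2.1 places the PFS primary analysis at about 33.5 months and the final analysis at about 96 months after first randomization.

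**Working it through.** The documents give no AESI resolution figure, so there is nothing to reproduce. The check has three parts.

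**1. Can late end dates occur?**

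| For | Against |
|---|---|
| Protocol 8.3.1: AESIs and nonserious AEs followed to resolution or stabilization | Protocol 8.3: AEs recorded until 90 days after last dose or new anticancer therapy, whichever is first |
| Protocol 9.3, follow-up: AE kept open in the eCRF until resolved or judged permanent | Protocol 9.3, recording: no end date required if unresolved at the final safety follow-up |
| Protocol 9.4: AESIs followed to resolution, stabilization or explanation | Table 3: AEs not marked under efficacy or survival follow-up |
| Protocol 7.1.2: related toxicities followed past the visit if still open | Protocol 8.9.1: safety visit falls 90 days after EOT |

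Late end dates are therefore allowed but not scheduled.

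**2. Hand example.** Take 20 nonserious AESIs, with the window ending at day 200 for all. Ten resolve at days 20, 40, …, 200; one at day 300; one at day 400; eight never.

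- Day 200, any rule: 10/20 = 50% resolved, S = 0.50.
- SAP rule: the eight unresolved leave at day 200, so two remain. Day 300: S = 0.50 × 1/2 = 0.25, giving 75%. Day 400: S = 0.25 × 0/1 = 0, giving 100%.
- Following the eight past day 400: S = 0.50 × 9/10 = 0.45, giving 55%; then 0.45 × 8/9 = 0.40, giving 60%. This is the true 12/20.
- SAP rule with four of the eight serious, hence kept at risk: S = 0.50 × 5/6 = 0.417, giving 58.3%; then 0.417 × 4/5 = 0.333, giving 66.7%.
- Both sides capped at day 200: 50%, and no estimate beyond.

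**3. Simulation with assumed inputs** (none from the documents except the 336-day treatment length and the 90 days): 400,000 AESIs per row, onset uniform over 336 days, EOT at day 336 for all, cutoff 1 to 5 years after EOT, every resolution before cutoff recorded, exponential time to resolution among resolvers with median m, and a share p never resolving. The true rate at t days is (1 − p)(1 − 2^(−t/m)). For p = 0.4, m = 180, t = 730: 0.6 × (1 − 0.060) = 56.4%.

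| p | m (days) | Serious | True, 1/2/3 years (%) | SAP rule, 1/2/3 years (%) |
|---|---|---|---|---|
| 40% | 180 | none | 45.4 / 56.4 / 59.2 | 54.0 / 90.7 / 98.6 |
| 40% | 180 | half | 45.2 / 56.3 / 59.1 | 48.5 / 65.0 / 69.2 |
| 40% | 180 | all | 45.2 / 56.4 / 59.1 | 45.2 / 56.5 / 59.2 |
| 40% | 60 | none | 59.0 / 59.9 / 59.9 | 65.2 / 99.3 / 100.0 |
| 40% | 60 | half | 59.0 / 59.9 / 59.9 | 61.2 / 62.7 / 62.8 |
| 20% | 180 | none | 60.3 / 75.1 / 78.8 | 66.4 / 93.5 / 99.0 |
| 20% | 180 | half | 60.5 / 75.2 / 78.9 | 63.1 / 81.9 / 86.5 |
| 40% | 5 | none | 60.1 / 60.1 / 60.1 | 60.1 / 60.1 / 60.1 |

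In the first row, capping both sides returns the true 45.4% at 1 year. It gives no estimate past day 336 + 90 = 426 from onset.

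**The case against.** The strongest reply is that the window mirrors the AE schedule. A reader might infer that the 90-day limit has no basis in data collection. The documents do not support that: Protocol 8.3, the recording part of 9.3, Table 3 and 8.9.1 all point to a 90-day horizon. If those sections govern in practice, late end dates will be rare and the curve will simply end in censoring. This stands as a limit on size. It does not justify the asymmetry, because a 90-day horizon would require censoring late resolutions there too.

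A reader might also infer that beyond the window only resolvers remain at risk, so that the resolution rate is driven to 100%. That is not so in general. The planned curve does not separate serious from nonserious AESIs, and unresolved serious ones stay at risk to cutoff, study discontinuation or death. Nor is EOT + 90 days a single point on a time axis that starts at AESI onset, so the bias enters gradually.

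Reach is limited as well. Second primary malignancies are always serious (Protocol 9.2). Infusion reactions, CRS and TLS would usually resolve early, which is a clinical assumption the documents do not state. In the single-arm study of tafasitamab plus lenalidomide in DLBCL (Protocol 2.1.4.6), no participant had a Grade 3 or higher infusion reaction, TLS or CRS, so some AESIs may not exceed 10 participants. The summary involves no formal testing (SAP 8.1), and the same rule applies in both arms. All of this keeps the point minor.

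**Conclusion.** The rule is wrong as written, in a narrow place: nonserious AESIs in participants off treatment, with some resolutions recorded after the window. There censoring depends on the outcome, and late resolution rates are biased upward.

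The size rests on the share of nonserious events, how slowly they resolve, and whether late end dates are collected; the documents give none of these. In the assumed scenarios with half the events serious, the 3-year excess runs from 62.8 − 59.9 = 2.9 points to 69.2 − 59.1 = 10.1 points. Rates near 100% appear only when all or nearly all events are nonserious and some resolve late. The bias is nil for acute or all-serious AESIs. No efficacy conclusion is touched.

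**What to change.** In SAP 8.2.2, give nonserious AESIs in participants off treatment one horizon for events and censoring. The horizon stays the later of the safety follow-up visit and 90 days after EOT, with the existing truncation. Add one sentence: an AESI whose resolution date falls after the horizon is censored on it. State that no resolution rate will be reported for nonserious AESIs beyond the window. SAP 8.2.3 follows by reference.

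Following unresolved nonserious AESIs to data cutoff, study discontinuation or death, as for serious ones, is an alternative only if their status is actually collected after the safety visit. Censoring at the last status assessment is not a safe substitute: for many unresolved events that assessment is the safety visit itself, and the asymmetry would return.

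Reconcile Protocol 8.3, the recording part of 9.3 and Table 3 with Protocol 7.1.2, 8.3.1, the follow-up part of 9.3 and 9.4, so that the collection period for AESI end dates is clear.

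The cost is about one sentence in the SAP and no new data for the capped version. The downside is no estimate for nonserious AESIs beyond the window, and late resolution rates may look less favourable.

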8.2.3. Adverse Events of Special Interest by Category and Preferred Term

A second method will also be used to identify AESIs programmatically using SMQs, custom MedDRA queries, and/or selected PTs.

Adverse events of special interest for tafasitamab/placebo include:

- Standard MedDRA Queries
 - Tumour lysis syndrome
 - Hypersensitivity (≥ Grade 3)
- Preferred terms
 - Cytokine release syndrome
 - Second primary malignancy
 - Hepatitis B reactivation

Progressive multifocal leukoencephalopathy

Adverse events of special interest for lenalidomide include:

- Preferred term
- Second primary malignancy

The analysis of the AESI by category and PT will be carried out as described in Section 8.2.2.

A listing will display the complete selected category and PTs from custom MedDRA queries and/or the selected PTs, defined by the sponsor. This will be used as reference listing.

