9.1. Definition of Adverse Event

Adverse Event Definition

- An AE is any untoward medical occurrence associated with the use of a drug in humans, whether or not considered drug-related.
- An AE can therefore be any unfavorable or unintended sign (including an abnormal laboratory finding), symptom, or disease (new or exacerbated) temporally associated with the use of study treatment.

Additional Guidance for Events Meeting the Adverse Event Definition

- Any safety assessments (eg, ECG, vital signs measurements), including those that worsen from baseline, considered clinically significant in the medical and scientific judgment of the investigator (ie, not related to progression of underlying disease) are to be reported as an AE.
- Abnormal laboratory test results are to be reported as an AE if they are considered clinically meaningful, induce clinical signs or symptoms, require concomitant therapy, or require changes in study treatment. Whenever possible, a diagnosis (eg, anemia, thrombocytopenia) should be recorded in the eCRF rather than the abnormal laboratory test result (eg, low hemoglobin, platelet count decreased).
- Exacerbation of a chronic or intermittent pre-existing condition/disease, including either an increase in the frequency and/or intensity of the condition, is to be reported as an AE.
- New conditions detected or diagnosed after the start of study treatment administration are to be reported as an AE.
- Signs, symptoms, or the clinical sequelae of a suspected drug-drug interaction are to be reported as an AE.

- Signs and/or symptoms from dosing errors of a study treatment (eg, overdose) or a concomitant medication are to be reported as an AE.
- "Lack of efficacy," "disease progression," or "failure of expected pharmacological action" will not be reported as an AE or SAE. Such instances will be captured in the efficacy assessments.
- A condition that leads to a medical or surgical procedure (eg, endoscopy, appendectomy) will be reported as an AE if it occurs after obtaining informed consent. If the surgery procedure will be collected as well. If the condition is present before entering the study, then it should be captured as medical history.
- Pre-existing diseases or conditions with expected fluctuations in signs or symptoms should be reported as an AE only if the investigator judges the fluctuation to have worsened more than expected during study participation.

Events NOT Meeting the Adverse Event Definition

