9.5.1. Adverse Events of Special Interest by eCRF

Adverse events of special interest are defined as a subset of ECIs that an investigator should urgently communicate information about the event to the sponsor/designee for further evaluation. Communication can be in the form of eCRF entry, email, or phone call to the sponsor/designee.

Adverse events of special interest for tafasitamab/placebo are TLS, IRRs and allergic reactions to study drug ≥ Grade 3, CRS, SPM, hepatitis B reactivation, and PML.

Adverse events of special interest for lenalidomide are second primary malignancy.

Adverse events of special interest will be captured in the eCRF and if any of the serious criteria is met, should be captured as an SAE as well.

Adverse events of special interest should be reported as a diagnosis and should include the symptoms of the event as 1 event term. For example, IRR with symptoms of hives, chills, and fever.

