9.5.2. Adverse Events of Special Interest by Category and Preferred Term

A second method will be used to identify AESIs programmatically using standardized MedDRA queries, custom MedDRA queries, and/or selected preferred terms. The same high-level terms as

described in Section 9.5.1 will be used for this analysis; please refer the SAP for further specific details.

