- Age group ($< 65 \text{ vs} \ge 65 \text{ years}$, $< 75 \text{ vs} \ge 75 \text{ years}$), sex, race and MZL subtype (for MZL population only) will be displayed for the following tables:
 - Overall Summary of TEAEs
 - Summary of TEAEs by MedDRA SOC and PT
 - Summary of Serious TEAEs by MedDRA SOC and PT
 - Summary of Grade 3 or 4 TEAEs by MedDRA SOC and PT
 - Summary of TEAEs with a fatal outcome by MedDRA SOC and PT
- Creatinine Clearance (≥ 30 and < 60 ml/min vs ≥ 60) will be displayed for the following tables:
 - Overall Summary of TEAEs
 - Summary of TEAEs by MedDRA SOC and PT
 - Summary of Serious TEAEs by MedDRA SOC and PT
 - Summary of Grade 3 or 4 TEAEs by MedDRA SOC and PT
 - Summary of TEAEs with a fatal outcome by MedDRA SOC and PT
 - Summary of lenalidomide treatment related TEAEs by MedDRA SOC and PT
 - Summary of TEAEs leading to lenalidomide dose reduction by MedDRA SOC and PT
 - Summary of TEAEs leading to discontinuation of lenalidomide by MedDRA SOC and PT

In addition, the following summaries will be produced:

Selected hematological TEAEs (neutropenia, febrile neutropenia, anemia, thrombocytopenia) of Grade 3 or 4 and fatal by SOC, PT, and grade.

- PTs used to identify neutropenia: "neutropenia," "neutrophil count decreased"
- PTs used to identify anemia: "anemia," "red blood cell count decreased"
- PTs used to identify thrombocytopenia: "platelet count decreased,"
 "thrombocytopenia"
- PTs used to identify febrile neutropenia: "febrile neutropenia"

- Duration of TEAEs of the selected PTs and customized MedDRA queries:
 - Neutropenia ≥ Grade 3 (PTs "neutropenia," "neutrophil count decreased")
 - Thrombocytopenia ≥ Grade 3 (PTs "thrombocytopenia," "platelet count decreased")
 - Infections and infestations ≥ Grade 3 (SOC "infections and infestations")
 - Infective pneumonia ≥ Grade 3 (SMQ code 20000231, narrow scope)
 - Urinary tract infection ≥ Grade 3 (HLT "bladder infections and inflammations,"
 HLT "Genitourinary infections and inflammations NEC," HLT
 "Glomerulonephritis and nephrotic syndrome")
 - Sepsis ≥ Grade 3 (SMQ "sepsis" and SMQ "agranulocytosis")
 - Febrile neutropenia, all grades (PT "febrile neutropenia")
 - Thromboembolic event, all grades (SMQ code 2000081)
 - Thromboembolic event ≥ Grade 3 (SMQ code 2000081)
 - Opportunistic infections ≥ Grade 3 (SMQ "opportunistic infections")

Selected AEs included in the previous summaries will be listed as a reference.

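### SAP 8.2.3 names no infusion-related-reaction term in the programmatic AESI search, and the SAP 8.2.4 anemia group has no hemoglobin term, so the tables built on them may undercount

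*SAP*

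**What the plan says.** **AESI search.** Protocol 9.5.1 sets the categories to be flagged on the eCRF: those "for tafasitamab/placebo are TLS, IRRs and allergic reactions to study drug ≥ Grade 3, CRS, SPM, hepatitis B reactivation, and PML". Protocol 9.5.2 adds a programmatic search and ties it to the same list: "The same high-level terms as" those "described in Section 9.5.1 will be used for this analysis; please refer the SAP for further specific details". SAP 8.2.2, the eCRF method, repeats the protocol list with IRRs in it. SAP 8.2.3, the programmatic method, opens with "A second method will also be used to identify AESIs programmatically using SMQs, custom MedDRA queries, and/or selected PTs". For tafasitamab/placebo it then gives standardized queries for tumor lysis syndrome and "Hypersensitivity (≥ Grade 3" or higher), and preferred terms for cytokine release syndrome, second primary malignancy, hepatitis B reactivation and PML. No entry names an infusion-related reaction. SAP 10.1, which records departures from protocol-defined analyses, does not mention this one.

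**Anemia group.** SAP 8.2.4 defines the selected hematological events by fixed preferred-term lists. Under "PTs used to identify anemia" it gives *anemia* and *red blood cell count decreased*, and nothing else. Protocol 9.1 asks sites to record a diagnosis where they can, rather than a laboratory result, and its examples of such results are "low hemoglobin, platelet count decreased".

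**The concern.** The programmatic method identifies AESIs without relying on the site's flag, so its value lies in the events that sites did not flag. IRRs come first in the risks set out in Protocol 2.3 and have their own interruption and discontinuation rules in Protocol 6.5.2. A protocol category with no stated counterpart in this search weakens the cross-check for that category, and the SAP does not declare the change.

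The anemia group feeds the Grade 3 or 4 and fatal hematological tables (3.2.35 and 3.2.36), which readers are likely to use to compare cytopenias between arms. Applied as written, the list leaves out any event coded to a hemoglobin result. The two sibling groups would keep the equivalent event.

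**Working it through.** The plan gives no figure for either shortfall, so there is none to reproduce. The check is a term-by-term comparison, followed by two scale calculations that rest on stated assumptions.

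**1. AESI categories for tafasitamab/placebo**

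| Protocol 9.5.1 | SAP 8.2.2 (eCRF flag) | SAP 8.2.3 (programmatic) |
|---|---|---|
| Tumor lysis syndrome | present | standardized query |
| IRRs and allergic reactions, ≥ Grade 3 | present | hypersensitivity query, ≥ Grade 3; no IRR entry |
| Cytokine release syndrome | present | preferred term |
| Second primary malignancy | present | preferred term |
| Hepatitis B reactivation | present | preferred term |
| PML | present | preferred term |

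Five of the six groups have a direct counterpart. The sixth is a combined group, and only its allergic half is named.

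Two protocol passages bear on whether a hypersensitivity query could stand in for IRRs. The note to Table 8 lists allergic reaction/hypersensitivity as one possible sign of an IRR among many others, including rigors, hypotension, nausea and tumor pain, so IRR is the wider concept. Protocol 9.5.1 asks for an IRR to be reported as a single diagnosis that carries its symptoms, so hives within an IRR would not be a separate event for the query to find. Capture therefore depends on whether the query contains the IRR term itself, and the documents do not give the query's content.

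The grade limit is also unclear. The phrase in 9.5.1 can be read as applying ≥ Grade 3 to both IRRs and allergic reactions, or to allergic reactions only. On the second reading, a query cut at Grade 3 would exclude lower-grade IRRs even if it contained the term.

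**2. Hematological groups in SAP 8.2.4**

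| Group | Diagnosis term | Laboratory term | Analyte in Protocol Table 11? |
|---|---|---|---|
| Neutropenia | neutropenia | neutrophil count decreased | yes (white cell differential) |
| Thrombocytopenia | thrombocytopenia | platelet count decreased | yes |
| Anemia | anemia | red blood cell count decreased | no; hemoglobin and hematocrit are listed |

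The anemia group contains a term for an analyte that is not scheduled and omits the one that Protocol 9.1 uses as its example.

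**3. Scale for IRRs (assumption: ≥ Grade 3 applies to IRRs)**

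In the earlier tafasitamab plus lenalidomide trial (Protocol 2.1.4.6) no participant had a Grade 3 or higher IRR. The safety denominator is inferred: 41 / 0.506 = 81.03 and 30 / 0.37 = 81.08, so 81. The exact two-sided 95% upper limit for 0 of 81 is

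1 − 0.025^(1/81) = 0.0445, or 4.5%.

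With about 618 / 2 = 309 participants per arm, 309 × 0.0445 = 13.8. The range is therefore 0 to about 14 participants in the tafasitamab arm with such an event. This bounds the events in the category, not the number missed, which would be the part that sites did not flag and the query did not catch. That regimen had no rituximab, so the true range here may differ.

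**4. Scale for anemia**

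Let q be the share of participants with Grade 3 or 4 anemia recorded only under a hemoglobin term. The table captures 1 − q: 100% at q = 0, 90% at q = 10% and 80% at q = 20%. The documents give no value for q.

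**The case against.** The best defense on IRRs is that the protocol treats IRRs and allergic reactions as one group with a Grade 3 limit, and SAP 8.2.3 has one entry, in the matching place and with the same limit. The hypersensitivity query may be meant to cover both. The SAP list is also introduced as inclusive rather than exhaustive, and the section allows custom queries and sponsor-defined terms shown in a reference listing. This is a fair reading, and it rules out saying that the search cannot find IRRs. It does not close the gap: the SAP never says that the query covers IRRs, and a listing shows the terms chosen without committing the sponsor to any of them.

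On anemia, Protocol 9.1 and 8.3.1 tell sites to record the diagnosis, so an event is missed only when a site reports the laboratory result instead. That stands and limits the effect. But the instruction is qualified, and the SAP itself allows for laboratory terms in all three groups.

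It also stands that nothing is lost from the report as a whole. IRRs flagged by sites appear in the eCRF tables (3.2.31 and 3.2.32), both kinds of event appear in the tables by system organ class and preferred term, and hemoglobin appears in the hematology CTCAE shift table (3.3.3.1). No formal safety testing is planned, and the trial is double-blind with one term list for both arms.

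A reader might infer that every unflagged IRR is missed. The documents do not support this without the query's content. A reader might also apply an assumed miscoding share to the 37% anemia rate in Protocol 2.1.4.6. That rate has no Grade 3 restriction, whereas Tables 3.2.35 and 3.2.36 cover Grade 3 or 4 and fatal events, and no miscoding share is given, so the product would not estimate the shortfall.

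**Conclusion.** Both textual defects hold. SAP 8.2.3 departs from Protocol 9.5.2 by naming no IRR term, without declaring the change. The anemia list in SAP 8.2.4 is inconsistent with its siblings and with the protocol's laboratory panel. The supportable consequence is conditional. Tables 3.2.33 and 3.2.34 may miss unflagged IRRs if the hypersensitivity query does not contain the IRR term. Tables 3.2.35 and 3.2.36 may undercount anemia to the extent that sites report low hemoglobin.

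Neither size can be derived from the documents. The limit of about 14 per arm is only an indication of scale, resting on an inferred denominator, a regimen without rituximab and a Grade 3 limit on IRRs. It would go too far to conclude that the tables do undercount, or that the comparison between arms is biased: no mechanism that differs by arm is shown. The point concerns the safety summaries only and leaves the primary analysis untouched. It is worth correcting because the protocol sets the requirement and the correction is simple.

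**What to change.** Before unblinding:

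- In SAP 8.2.3, add an explicit infusion-related-reaction term, or state that the hypersensitivity query contains it. Say whether the Grade 3 limit applies to IRRs, in line with what Protocol 9.5.1 intends.
- In SAP 8.2.4, add the hemoglobin-decrease preferred term to the anemia group.
- Update the reference listings of selected terms (Listings 2.7.13 and 2.7.14) to match.

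The cost is a few lines of SAP text and an edit to the term-list file, with no new data collection. Settling the terms before unblinding also keeps the choice from being challenged as made after seeing the results.
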